9.0 Statistical design with exploratory endpoints –

The primary efficacy endpoint is IgG response, defined as having improvement in IgG level by at least 25% at 6 months, compared to baseline. We are targeting an IgG response rate of 50% and we would not be interested in pursuing further if the IgG response rate is 20% or lower. Using Simon's optimal two-stage design, we will enroll 12 patients in the first stage and the trial will be stopped if there are 3 or less IgG responders among the first 12 patients. If there are 4 or more responders, we will continue the enrollment until 31 patients are reached. The effect of lenalidomide is demonstrated and worth pursuing further if among the total 31 patients, at least 10 patients achieve IgG response. This design is based on a type I error rate of 0.025 and a 90% power. Under the null hypothesis, the probability of early termination is 79% and the expected sample size is 16 patients. Patient enrollment will be suspended if there are not at least 3 IgG responders in the first 12 patients and not all 12 patients have been evaluated at 6 months. To account for a potential 10% early drop-out rate, we will enroll 35 patients so as to have 31 patients with both baseline and 6-month evaluations on IgG. Potential reasons for early dropouts are patients' choice, inability to return to our center or changes in CLL status that may require a different intervention. Sensitivity

analysis will be performed to assess the impact of early dropouts. For example, we will analyze the data counting early dropouts either as "failures" (the most conservative approach) or as "missing" (thus, excluded from the analysis) and evaluate the response rate in both scenarios. Also, since the treatment requires at least 3 months of therapy before seeing an effect on immunoglobulin levels, we will also perform a secondary analysis by including only those patients who have been treated for at least 3 months, while counting those early dropouts between 3 and 6 months as "failures".

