9.0 Statistical design with exploratory endpoints –

The primary efficacy endpoint is IgG response, defined as having improvement in IgG level by at least 25% at 6 months, compared to baseline. We are targeting an IgG response rate of 50% and we would not be interested in pursuing further if the IgG response rate is 20% or lower. Using Simon's optimal two-stage design, we will enroll 12 patients in the first stage and the trial will be stopped if there are 3 or less IgG responders among the first 12 patients. If there are 4 or more responders, we will continue the enrollment until 31 patients are reached. The effect of lenalidomide is demonstrated and worth pursuing further if among the total 31 patients, at least 10 patients achieve IgG response. This design is based on a type I error rate of 0.025 and a 90% power. Under the null hypothesis, the probability of early termination is 79% and the expected sample size is 16 patients. Patient enrollment will be suspended if there are not at least 3 IgG responders in the first 12 patients and not all 12 patients have been evaluated at 6 months. To account for a potential 10% early drop-out rate, we will enroll 35 patients so as to have 31 patients with both baseline and 6-month evaluations on IgG. Potential reasons for early dropouts are patients' choice, inability to return to our center or changes in CLL status that may require a different intervention. Sensitivity

analysis will be performed to assess the impact of early dropouts. For example, we will analyze the data counting early dropouts either as "failures" (the most conservative approach) or as "missing" (thus, excluded from the analysis) and evaluate the response rate in both scenarios. Also, since the treatment requires at least 3 months of therapy before seeing an effect on immunoglobulin levels, we will also perform a secondary analysis by including only those patients who have been treated for at least 3 months, while counting those early dropouts between 3 and 6 months as "failures".

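### The final rule of at least 10 responders among 31 has a type I error of 0.051, not 0.025 (at least 11 is needed), and no rule covers the other evaluable numbers that enrolling 35 can produce

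*Protocol*

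**What the plan says.** Section 9.0 of the Protocol, which the SAP repeats, sets out a Simon optimal two-stage design for the 6-month IgG response rate.

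- **Null rate, 20%:** "we would not be interested in pursuing further if the IgG response rate is 20% or lower". The target rate is 50%.
- **Stage 1:** "the trial will be stopped if there are 3 or less IgG responders among the first 12 patients".
- **Stage 2:** with 4 or more responders, "we will continue the enrollment until 31 patients are reached".
- **Success:** the effect is taken as shown "if among the total 31 patients, at least 10 patients achieve IgG response".
- **Stated properties:** "This design is based on a type I error rate of 0.025 and a 90% power". Under the null, "the probability of early termination is 79% and the expected sample size is 16 patients".
- **Enrolment:** "To account for a potential 10% early drop-out rate, we will enroll 35 patients", the aim being 31 with both a baseline and a 6-month IgG value.

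Sensitivity analyses count early dropouts as failures or leave them out. A secondary analysis keeps only patients treated for at least 3 months. The section does not say which of these sets drives the go/no-go decision. It gives no cut-off for an evaluable number other than 31.

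**The concern.** There are two separate problems in the same paragraph.

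First, the cut-off and the stated error rate do not belong to the same design. If the cut-off is one responder too low, a drug with a true 20% response rate is declared worth pursuing more often than the plan says.

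Second, the decision rule exists for one sample size only, while the enrolment plan will usually produce another. One sentence ends enrolment at 31 and another takes it to 35. If 33 patients turn out to be evaluable, the plan does not say whether all 33 count, whether only 31 count and which ones, or whether the cut-off moves. In an open single-arm trial that choice could be made after the responses are known.

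**Working it through.** **Inputs (Section 9.0):** null rate 0.20, target rate 0.50; first stage of 12, continue at 4 or more; total 31, success at 10 or more; stated type I error 0.025 and power 90%; 35 enrolled, 10% dropout.

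**Formula.** For total N and cut-off s, the probability of declaring success at response rate p is

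P(N, s, p) = sum over x = 4 to 12 of P[Bin(12, p) = x] × P[Bin(N − 12, p) ≥ s − x].

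The type I error is P at p = 0.20 and the power is P at p = 0.50. The first stage is taken as 12 evaluable patients throughout.

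**Step 1: the figures that reproduce.**
- Early termination under the null: P[Bin(12, 0.20) ≤ 3] = 0.795 (stated 79%).
- Expected size under the null: 12 + (1 − 0.795) × 19 = 15.9 (stated 16).
- Enrolment: 31 / 0.90 = 34.4, rounded up to 35.

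**Step 2: the written cut-off, at least 10 of 31.** Terms for x = 4, 5, 6, 7, 8, 9:

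0.13288 × 0.16306 + 0.05315 × 0.32671 + 0.01550 × 0.54491 + 0.00332 × 0.76311 + 0.00052 × 0.91713 + 0.00006 × 0.98559
= 0.02167 + 0.01736 + 0.00845 + 0.00253 + 0.00048 + 0.00006 = 0.0506 (0.05055 before rounding the terms).

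Power is 0.921. The stated 0.025 is not reproduced; the actual value is about twice as large.

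**Step 3: at least 11 of 31.**

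0.13288 × 0.06760 + 0.05315 × 0.16306 + 0.01550 × 0.32671 + 0.00332 × 0.54491 + 0.00052 × 0.76311 + 0.00006 × 0.91713 = 0.0250 (0.02498 before rounding).

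Power is 0.908. An exhaustive search for the Simon optimal design at type I error 0.025 and power 0.90 returns exactly this one: 12 patients, stop at 3 or fewer, 31 in total, success at 11 or more. That design rejects the treatment at 10 or fewer, so the written 10 looks like the rejection bound used as a success bound. That origin is an inference.

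**Step 4: how many will be evaluable.** If each of 35 patients drops out independently with probability 0.10, the evaluable number is Bin(35, 0.90). It is 32 or more with probability 0.531, exactly 31 with probability 0.200, and fewer with probability 0.269.

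**Step 5: other evaluable numbers.**

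| Evaluable N | Probability | Type I error, ≥10 | Type I error, ≥11 | Power, ≥11 | Type I error, ≥12 | Power, ≥12 |
|---|---|---|---|---|---|---|
| 28 | 0.035 | 0.0305 | 0.0127 | 0.868 | 0.0045 | 0.802 |
| 29 | 0.077 | 0.0367 | 0.0163 | 0.886 | 0.0062 | 0.835 |
| 30 | 0.138 | 0.0434 | 0.0204 | 0.899 | 0.0082 | 0.861 |
| 31 | 0.200 | 0.0506 | 0.0250 | 0.908 | 0.0106 | 0.880 |
| 32 | 0.225 | 0.0580 | 0.0301 | 0.914 | 0.0135 | 0.894 |
| 33 | 0.184 | 0.0657 | 0.0357 | 0.919 | 0.0168 | 0.904 |
| 34 | 0.097 | 0.0735 | 0.0417 | 0.922 | 0.0206 | 0.911 |
| 35 | 0.025 | 0.0815 | 0.0481 | 0.924 | 0.0248 | 0.917 |

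Weighting the type I error by the full dropout distribution gives 0.055 for a cut-off of 10 and 0.028 for a cut-off of 11. At 11 of 31 there is no headroom (0.02498), so a single extra evaluable patient takes the value above 0.025.

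**The case against.** The strongest reply concerns the second problem. The text speaks of a total of 31 and enrols 35 so as to have 31 with both IgG evaluations. A natural reading is that 31 evaluable patients form the decision set and 35 is only the allowance for reaching it. On that reading the type I error stays at its 31-patient value. The toxicity operating characteristics also use 35 as the maximum throughout, so few readers would really stop enrolment at 31.

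The residual effect is also small. With the cut-off corrected to 11, the average is 0.028 against 0.025, and the 0.048 at 35 requires no dropouts at all, which has probability 0.9^35 = 2.5%. If dropouts counted as failures among all 35, with dropout independent of response, the null rate would be 0.20 × 0.90 = 0.18, and at least 11 of 35 would give 0.0245, which is no inflation.

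Most of this stands, and it limits the size of the second problem. It does not close it. The text never says that only the first 31 evaluable patients count, and the dropout analyses are labelled sensitivity or secondary without naming the set for the decision. None of it touches the first problem, since the written cut-off misses 0.025 at exactly 31.

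A reader might infer that enrolling 35 is what breaks the error rate, so that 0.025 holds at 31 and is exceeded whenever 32 to 35 are evaluable. The documents do not support that. The written rule gives 0.051 at 31 and 0.031 to 0.043 at 28 to 30, so the cut-off is the main cause. The further rise at 32 to 35 occurs only if the cut-off is carried over unchanged to all evaluable patients, and the plan does not say that it will be.

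**Conclusion.** The concern holds in two parts.

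1. **Cut-off.** The only final rule has an exact type I error of 0.051 at 31 patients, about double the stated 0.025. At least 11 of 31 gives 0.02498 with power 0.908 and agrees with every other stated property. This rests only on the design figures in Section 9.0, with 12 evaluable patients in the first stage.
2. **Decision set.** The plan leaves open what happens at any evaluable number other than 31, although 31 itself has a probability of only about one in five. This assumes independent 10% dropout among 35. If a cut-off of 11 were applied to all evaluable patients, the type I error would be 0.030 to 0.048 at 32 to 35 and 0.028 on average, a modest excess. If only the first 31 count, there is none.

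The right description of the second part is that the rule is not specified, rather than that the error rate is necessarily exceeded. Both parts should be settled before the data are analysed.

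**What to change.** 1. In both documents, change the success cut-off to at least 11 responders among 31.
2. State that the decision uses the first 31 evaluable patients in order of enrolment, evaluable meaning a baseline and a 6-month IgG value. Patients beyond 31 still contribute to estimation. If fewer than 31 are evaluable, keep 11: the type I error is then below 0.025 (0.013 to 0.020 at 28 to 30).
3. Alternatively, tabulate cut-offs in advance: at least 11 for 28 to 31 evaluable (type I error 0.013 to 0.025, power 0.868 to 0.908) and at least 12 for 32 to 35 (type I error 0.0135 to 0.0248, power 0.894 to 0.917). This covers 98% of outcomes under the 10% dropout model.
4. Reword the enrolment sentence to say that enrolment continues until 31 evaluable patients are reached, with up to 35 enrolled.

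The cost is a few sentences or a short table, with no extra patients. Moving from 10 to 11 lowers power at 31 from 0.921 to 0.908, still above the planned 90%. With the table, power is slightly under 0.90 at 28 to 30 and at 32 evaluable. The first-31 rule avoids the loss at 32 but not at 28 to 30.

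### The success cut-off of at least 10 of 31 responders is one too low: it gives a type I error of 5.1%, not the stated 2.5%

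*Protocol*

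**What the plan says.** Protocol section 9.0 fixes every element of the design, and the SAP carries the same text.

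- Uninteresting rate: "we would not be interested in pursuing further if the IgG response rate is 20% or lower". The target response rate is 50%.
- Design and stage 1: a Simon optimal design in two stages, with 12 patients in stage 1. The stopping rule is: "the trial will be stopped if there are 3 or less IgG responders among the first 12 patients". With 4 or more responders, enrolment continues to 31.
- Final rule: "The effect of lenalidomide is demonstrated and worth pursuing further if among the total 31 patients, at least 10 patients achieve IgG response". The SAP has the same cut-off: "if among the total 31 patients, at least 10 patients achieve IgG response".
- Error rates: "This design is based on a type I error rate of 0.025 and a 90% power".
- Operating characteristics: "Under the null hypothesis, the probability of early termination is 79% and the expected sample size is 16 patients".

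**The concern.** In the usual notation for a Simon design, each bound is the largest number of responders that still counts as failure. A design written 3/12, 10/31 therefore stops at 3 or fewer of 12 and succeeds only with more than 10 of 31, that is, at least 11. The plan converts the first bound correctly (3 or fewer stops, 4 or more continues) but gives the final bound as at least 10. That suggests the final bound was carried over without the same conversion. The documents do not confirm this cause, and the finding does not depend on it.

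This cut-off is the only final decision rule stated for the primary endpoint of a single-arm trial. If it is one too low, a drug at the rate the sponsor regards as not worth pursuing is declared effective more often than the plan says. A result of exactly 10 of 31 would be a success under the written rule and a failure under the design the plan names. Settling that after the data are seen would not be credible.

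**Working it through.** **Inputs, all from protocol section 9.0:** p0 = 0.20, p1 = 0.50; stage 1 n1 = 12, stop if 3 or fewer respond; total n = 31, so 19 patients in stage 2; success if at least c = 10 respond; stated type I error 0.025 and power 0.90.

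**Step 1. Figures that reproduce.** At p = 0.20 the probability of early termination is P(X1 ≤ 3 | 12, 0.20) = 0.0687 + 0.2062 + 0.2835 + 0.2362 = 0.7946, matching the stated 79%. The expected sample size is 12 + 19 × (1 − 0.7946) = 15.90, matching the stated 16. Neither figure involves c.

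**Step 2. Type I error of the rule as written.** The probability of declaring success is

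Σ (x1 = 4 to 12) P(X1 = x1 | 12, p) × P(X2 ≥ c − x1 | 19, p).

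At p = 0.20:

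| x1 | P(X1 = x1) | P(X2 ≥ 10 − x1) | Product, c = 10 | P(X2 ≥ 11 − x1) | Product, c = 11 |
|---|---|---|---|---|---|
| 4 | 0.13288 | 0.16306 | 0.02167 | 0.06760 | 0.00898 |
| 5 | 0.05315 | 0.32671 | 0.01736 | 0.16306 | 0.00867 |
| 6 | 0.01550 | 0.54491 | 0.00845 | 0.32671 | 0.00506 |
| 7 | 0.00332 | 0.76311 | 0.00253 | 0.54491 | 0.00181 |
| 8 | 0.00052 | 0.91713 | 0.00048 | 0.76311 | 0.00040 |
| 9 or more | 0.00006 | – | 0.00006 | – | 0.00005 |
| Sum (before rounding) | | | **0.05055** | | **0.02498** |

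**Step 3. Both error rates by cut-off** (same sum at p = 0.50 for power):

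| Success if at least | Type I error | Power | Meets 0.025 and 90%? |
|---|---|---|---|
| 10 (as written) | 0.0506 | 0.921 | No: type I error too high |
| 11 | 0.02498 | 0.908 | Yes |
| 12 | 0.0106 | 0.880 | No: power too low |

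**Step 4. Which design was intended.** A search over all two-stage designs up to n = 45 with type I error at most 0.025 and power at least 0.90, minimising expected sample size at p0, returns n1 = 12, stop at 3 or fewer, n = 31, success at 11 or more. Every stated element of the plan matches this except the final cut-off.

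**Step 5. Other readings.**

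- Type I error of 0.05 intended: the written rule still slightly exceeds it (0.0506). The optimal design would be a different one: stop at 2 or fewer of 10, total 22, success at 8 or more, expected sample size 13.9.
- Stage 1 stop at 2 or fewer: type I error 0.0665.
- No interim stop: 0.0746.
- All 35 enrolled patients counted, cut-off 10: 0.0815.

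None brings a cut-off of 10 to 0.025.

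**Step 6. Where the two rules part.** They differ only if exactly 10 of 31 respond after stage 1 is passed. The probability of that is 0.0506 − 0.0250 = 0.026 at a true rate of 20%, and 0.089, 0.062 and 0.013 at 30%, 40% and 50%.

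**The case against.** The arithmetic is not in dispute; the best case on the other side is about weight.

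- **One outcome only.** The rules differ at a single count, with probability no more than about 0.09 at the rates examined. The stage 1 stop, which ends 79% of trials under the null, is unaffected. The absolute excess in type I error is 2.6 percentage points. All of this is true.
- **The interval would show the doubt.** The primary analysis is a response rate with a 95% confidence interval. At 10 of 31 the ordinary exact interval is about 17% to 51%, so a reader would see that 20% is not excluded. But section 9.0 still says the effect is demonstrated at 10. The interval is also not a working substitute for the rule: at 11 of 31 its lower limit is 19.2%, ignoring the two-stage design.
- **The error rate could be restated instead.** The contradiction is between the cut-off and the stated type I error, and the sponsor could change the latter to about 5.1%. That would be consistent, but the rule would then no longer be the optimal design the plan names, and every other figure in the paragraph points to 0.025.
- **A cut-off of 11 is exact only at 31.** The plan enrols 35 to obtain 31. With stage 1 unchanged, at least 11 responders gives a type I error of 0.030 with 32 evaluable patients and 0.048 with 35; with 30, power is 0.899. This stands as a limit on the correction. It does not support a cut-off of 10, which has a higher type I error at each of these numbers.

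**Conclusion.** The final success rule is wrong as written. With exactly 31 evaluable patients and the stated stage 1 rule, its type I error is 0.0506 against a stated 0.025: an absolute excess of 0.026, or about double. The stated power of 90% is met (0.921), and the early-termination and expected-sample-size figures are correct. The result needs only the plan's own inputs and the usual assumption of independent patients with a common response probability. It makes no claim about other evaluable numbers. The discrepancy is a single responder, but it sits in the primary success criterion, so it should be corrected before the result is known.

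**What to change.** In protocol section 9.0 and the matching SAP text, change the final cut-off from at least 10 to at least 11 of 31. Type I error is then 0.02498 and power 0.908, so both stated rates hold. Stage 1, total enrolment, early-termination probability and expected sample size stay the same. The cost is 0.921 − 0.908 = 0.013 in power and one number in each document.

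If the sponsor prefers to keep 10, the text should instead state a type I error of about 5.1% and no longer describe the rule as an optimal design at 0.025.

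### The enrolment hold while stage 1 results are pending uses a threshold of 3 responders, but the stage 1 rule needs 4 to continue (minor inconsistency)

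*Protocol*

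**What the plan says.** Section 9.0 of the protocol sets a Simon two-stage design with 12 patients in stage 1 and 31 in total. Three sentences govern the same 12 patients and the same 6-month IgG endpoint:

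- Stop: "the trial will be stopped if there are 3 or less IgG responders among the first 12 patients".
- Continue: "If there are 4 or more responders, we will continue the enrollment until 31 patients are reached".
- Hold while results are outstanding: "Patient enrollment will be suspended if there are not at least 3 IgG responders in the first 12 patients", joined to the condition "and not all 12 patients have been evaluated at 6 months".

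The null rate is set by "we would not be interested in pursuing further if the IgG response rate is 20% or lower", and the target rate is 50%. The plan gives its own operating characteristics: "Under the null hypothesis, the probability of early termination is 79% and the expected sample size is 16 patients". The SAP repeats this text and does not resolve the difference.

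**The concern.** A hold on accrual before an interim look is meant to keep further patients out until continuation is assured. Under this plan, continuation is assured at the fourth responder. At the third it is not, because 3 of 12 is a stopping result. As written, the hold does not apply once 3 responders are seen, even if several of the 12 are still awaiting their 6-month evaluation, and no other sentence deals expressly with that state.

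At stake is the number of patients enrolled and treated in a trial that its own futility rule then stops. The statistical decision at stage 1 is not at stake.

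**Working it through.** **Inputs.** From section 9.0: null rate 0.20, target rate 0.50, stage 1 size 12, stop at 3 or fewer, total 31 (so 19 in stage 2), endpoint at 6 months. The documents give no accrual rate. I assume even accrual at *a* = 0.25, 0.5, 1 or 2 patients per month, with results arriving in order of enrolment.

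**1. Which threshold do the plan's own figures use?** Let X be Binomial(12, 0.20).

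- Stop at 3 or fewer: P(X ≤ 3) = 0.7946. Expected size = 12 + 19 × (1 − 0.7946) = 15.90. These are the stated 79% and 16.
- Stop at 2 or fewer (3 enough to continue): P(X ≤ 2) = 0.5583. Expected size = 12 + 19 × 0.4417 = 20.39. Neither matches.

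The design is therefore 4 to continue. The second line only identifies the boundary. It is not an effect of the hold sentence, which does not change the stop rule.

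**2. How often does the literal hold leave accrual open in a trial that then stops?** If results arrive one at a time, this needs 3 responders among the first 11 results and a non-responder in the last:

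C(11,3) × p³ × (1 − p)⁹ = 165 × p³ × (1 − p)⁹

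If the last *k* results arrive together, the three responders must fall in the first 12 − *k*, giving C(12 − k, 3) × p³ × (1 − p)⁹.

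| Last results arriving together | p = 0.20 | p = 0.50 |
|---|---|---|
| 1 (one at a time) | 0.177 | 0.040 |
| 2 | 0.129 | 0.029 |
| 3 | 0.090 | 0.021 |

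The one-at-a-time row is the upper end. It holds for any order of evaluation that is unrelated to response.

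**3. How many extra patients?** Let T be the position of the third responder, given exactly 3 of 12. Accrual resumes at the later of 12/a and T/a + 6 months, and the last result arrives at 12/a + 6. The excess is min(6a, 12 − T).

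| Accrual per month | Mean excess per affected trial | Mean over all trials, p = 0.20 | Mean over all trials, p = 0.50 |
|---|---|---|---|
| 0.25 | 1.36 | 0.24 | 0.06 |
| 0.5 | 2.24 | 0.40 | 0.09 |
| 1 | 2.91 | 0.52 | 0.12 |
| 2 | 3.00 | 0.53 | 0.12 |

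The averages over all trials are the per-trial excess times 0.177 or 0.040. At the null, expected enrolment moves from 15.90 to between 15.90 + 0.24 = 16.14 and 15.90 + 0.53 = 16.43, which still rounds to 16.

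**4. What does a hold at 4 cost?** In trials that pass stage 1, the delay is the reopening time at the fourth responder minus that at the third, each the later of 12/a and T/a + 6 with T the position of that responder. For *a* = 0.25, 0.5, 1 and 2 the mean delay is 0.36, 0.59, 1.13 and 0.93 months at p = 0.50, and 1.57, 1.97, 2.08 and 1.21 months at p = 0.20.

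**The case against.** The best reply is that the sentences can be read together. Stage 1 enrols 12 patients and enrolment continues only with 4 or more responders, so patient 13 always needs 4. On that reading nobody extra is enrolled. This is a fair reading and it limits the point. It also leaves the hold sentence with no work to do and still carrying a number that disagrees with the rule it serves.

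A second reply is that a lower hold may be deliberate, to avoid pausing a trial that will probably pass. At a 50% response rate, a trial with 3 responders and two results pending passes with probability 1 − 0.5² = 0.75. At 20% the same trial passes with probability only 1 − 0.8² = 0.36. No such rationale is stated in either document, so it remains a possibility and not an explanation.

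A third reply is that the effect is small and rests on an accrual rate the plan does not give. That stands, and the size is stated accordingly.

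A reader might also infer that the stage 1 rule is ambiguous between 3 and 4, or that the 79% or the error rates are disturbed. The documents do not support this. The stop and continue sentences are explicit, the stated figures follow from them, and the stop rule still applies once all 12 patients are evaluated.

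**Conclusion.** The point holds as a minor internal inconsistency. The hold threshold of 3 does not match the 4-to-continue rule, and the plan's own 79% and 16 show that the hold sentence is the one to change.

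Whether patients are exposed depends on the reading. If patient 13 always needs 4 responders, there is no extra exposure and only the number is wrong. On the literal reading, the chance that accrual stays open and stage 1 then fails is at most 17.7% at a 20% response rate and at most 4.0% at 50%. The excess is then a few patients per affected trial, and about half a patient or less averaged over all trials at the null. The probabilities assume that the order of results is unrelated to response. The patient counts also rest on the assumed even accrual of 0.25 to 2 per month.

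It would go too far to say that the trial will over-enrol. The text permits it in one state and does not require it.

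**What to change.** In protocol section 9.0 and in the SAP, change 3 to 4 in the suspension sentence and tie it to the 12th enrolment. For example: once the 12th patient has been entered, accrual is suspended until either 4 or more IgG responders have been recorded among those 12 or all 12 have had the 6-month evaluation. Keep the existing stop rule of 3 or fewer among 12.

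The drafting cost is one number and a short clause in two places. The operational cost is a later reopening in trials that pass stage 1: a mean of 0.4 to 1.1 months at a 50% response rate and 1.2 to 2.1 months at 20%, under the same accrual assumption. These are means. Individual trials may have no pause or a longer one.

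How stage 1 dropouts are counted or replaced is a separate design choice and is not part of this change.

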6.0 Evaluation during the Study

Complete blood counts (white blood cell, hemoglobin, platelets and differential), serum chemistry, basic metabolic profile, (sodium, potassium, chloride, CO₂, BUN, creatinine and glucose) will be monitored once every two-four weeks (+/- 4 days) while on lenalidomide.

At 3 months (+/- 3 weeks), patients will have a physical examination, CBC with differential and chemical survey, serum beta-2-microglobulin and IgA, IgG, IgM levels, flow cytometry (CD4+, CD8+). Pregnancy tests for females of childbearing potential and Risks of Fetal Exposure, Pregnancy Testing Guidelines and Acceptable Birth Control Methods, will be discussed with the patients.

Pneumococcal vaccination: Serum levels of antipneumococcal capsular polysaccharide antibodies will be measured before, 4 weeks (+/- 2 week) and 3 months (+/- 3 weeks) after vaccination and at the end of the study (to assess sustainable antibody responses) by ELISA. Influenza vaccination: Haemagglutination inhibition antibody titres (HAI) will be assessed by WHO influenza reagent kit before, 4 weeks (+/- 2 week) and 3 months

(+/- 3 weeks) after vaccination and at end of the study (to assess sustainable antibody responses) [12]. Influenza specific quantitative and qualitative CD8+ and CD4+ T cell responses will be determined by multiparameter flow cytometry techniques from stored PBMC's from the patients before vaccination, 4 weeks (+/- 2 week) and 3 months (+/- 3 weeks) after vaccination [13, 14]. Serum samples for cytokine levels (properdin, IFN- γ , IL-10, TNF- α , BAFF, IL-8, CCL3, and CCL4) will be stored before influenza vaccination at 4 weeks (+/- 2 week), 3 months (+/- 3 weeks) and at the end of the study). PBMC's will be stored at baseline, 4 weeks (+/- 2 week) and 3 months (+/- 3 weeks) after influenza vaccination to determine by multiparameter flow cytometry technique changes in influenza specific quantitative (using HLA-A2 restricted FluMP pentamer) and qualitative (using CD107a, IFN-gamma, IL-2 and TNF-alpha by intracellular staining) CD8+ and CD4+ T cell responses, as described [15].

Criteria for study discontinuation:

Treatment with study drug is discontinued and the patient will be removed from study when any of the following occurs:

1. Lack of response
2. Adverse event(s) that in the judgment of the investigator or the patient may cause severe or permanent harm or which rule out continuation of the study drug
3. Withdrawal of consent
4. Lost to follow-up

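### The go/no-go rule is sized on patients who reach the month-6 IgG, and nothing says how earlier dropouts count at either boundary

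*Protocol*

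**What the plan says.** Section 9.0 of the protocol, repeated word for word in the SAP, sets a two-stage rule. At stage 1, "the trial will be stopped if there are 3 or less IgG responders among the first 12 patients". The drug is judged worth pursuing "if among the total 31 patients, at least 10 patients achieve IgG response". The uninteresting rate is 20% ("we would not be interested in pursuing further if the IgG response rate is 20% or lower") and the target is 50%. The stated type I error is 0.025 and the stated power is 90%.

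The allowance for losses is 10%: "we will enroll 35 patients so as to have 31 patients with both baseline and 6-month evaluations on IgG". Three reasons for early dropout are listed: patient choice, inability to return to the centre, and "changes in CLL status that may require a different intervention". The discontinuation criteria in Section 6.0 open with "Treatment with study drug is discontinued and the patient will be removed from study when any of the following occurs", and the list that follows includes adverse events and lack of response.

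Dropouts are not ignored. Section 9.0 plans sensitivity analyses "counting early dropouts either as 'failures' (the most conservative approach) or as 'missing", and looks at the response rate both ways. A further secondary analysis is limited to patients treated for at least 3 months and counts those lost between months 3 and 6 as failures. The primary analysis is the IgG response rate with a 95% confidence interval, and no analysis population is named for it.

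**The concern.** The 31 patients in the success rule and the 31 with both IgG measurements appear to be the same set, with four extra enrolments to fill the gaps. A patient who leaves before month 6 because the CLL changed or because of toxicity would then be outside the denominator, although that patient has not achieved the response that the trial seeks. Removing likely non-responders can only push the observed rate up.

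The sensitivity analyses would show the effect but do not settle the decision, because the plan gives no rule for the case where they disagree. Ten responders among 31 evaluable patients meet the written criterion. The same ten among 35 enrolled are 10/35 = 28.6%, and no cut-off is stated for that denominator. At stake is the probability of recommending further development when the true rate among all treated patients is only 20%.

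**Working it through.** **Inputs from Section 9.0.** Null rate 0.20; target rate 0.50; stage 1 n = 12, continue with 4 or more responders; final n = 31, success with 10 or more; dropout d = 0.10; 35 enrolled. **Not in the documents:** the share f of dropouts who are true non-responders. I vary it from 0 to 1 and let the remaining dropouts respond like completers.

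**Formula.** For success at k or more of n:

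P(success) = Σ over x = 4 to 12 of P(X₁ = x) × P(X₂ ≥ k − x), with X₁ ~ Bin(12, p) and X₂ ~ Bin(n − 12, p).

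**Step 1: the plan's own figures (p = 0.20, no dropout).**
- Early termination: P(X₁ ≤ 3) = 0.7946. The stated 79% reproduces.
- Expected size: 12 + (1 − 0.7946) × 19 = 15.9. The stated 16 reproduces.
- Enrolment: 31/0.9 = 34.4, rounded up to 35. This reproduces.
- Type I error at 10 or more of 31: 0.0506. The stated 0.025 does **not** reproduce.
- Type I error at 11 or more of 31: 0.02498, with power 0.908. This matches the stated 0.025 and 90%. Power at 10 or more is 0.921.

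The stated error rate therefore belongs to a cut-off of 11. That mismatch is a separate matter, so both cut-offs are carried through below to keep it apart from the dropout effect.

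**Step 2: completer rate when the rate among all enrolled is 20%.** The overall rate is (1 − d)p_c + d(1 − f)p_c = p_c(1 − df), so p_c = 0.20/(1 − 0.10f). For f = 1 this is 0.20/0.90 = 0.222.

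**Step 3: false-positive rate if both boundaries are applied to completers.** Ratios are to the f = 0 row of the same column.

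| Share f | Completer rate | ≥10 of 31 | ≥11 of 31 |
|---|---|---|---|
| 0 | 0.200 | 0.0506 | 0.0250 |
| 1/3 | 0.207 | 0.0613 (×1.21) | 0.0314 (×1.26) |
| 1/2 | 0.211 | 0.0675 (×1.34) | 0.0352 (×1.41) |
| 1 | 0.222 | 0.0904 (×1.79) | 0.0498 (×1.99) |

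**Step 4: an alternative reading of stage 1.** Suppose the first 12 are 12 enrolled patients responding at 20%, and only the later 19 are completers at 22.2%. The f = 1 values fall to 0.0664 (×1.31) at ≥10 and 0.0358 (×1.43) at ≥11.

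**Step 5: all treated patients, missing month-6 IgG counted as non-response.** Continue with 4 or more of 12; success with 12 or more of 35.
- Type I error at 0.20: 0.0248.
- Power at 0.50: 0.917.
- Power if 50% holds only among the 90% who stay (0.50 × 0.90 = 0.45): 0.830.

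**The case against.** No sentence declares that the decision uses completers only. The statement about 35 and 31 patients is a sizing statement, the primary analysis names no population, and analysing dropouts as failures is planned. A reader might infer that the decision is bound to follow the more favourable count. The documents do not say so; they leave open which count governs. That part of the objection stands, and it is why the point is framed as a missing rule.

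A reader might also infer that dropout doubles the false-positive rate. That needs the full 10% dropout, every dropout a true non-responder, completer counting at both stages, and a cut-off of 11. Two of the three listed reasons are not disease-related, and with one third to one half of dropouts failing the increase is ×1.2 to ×1.4. Setting 0.090 against the stated 0.025 would mislead as well, because the cut-off mismatch alone already brings the rate to 0.051.

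Lack of response as a removal reason is weak evidence. Section 3.0 gives patients without IgG improvement at 3 months a further 3 months of treatment, and Section 8.0 judges response at 6 months. Most such patients would have a month-6 value and count as non-responders. Adverse events and change in CLL status carry the argument.

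Finally, analysing evaluable patients in a single-arm phase 2 trial is partly a matter of preference, and one sentence naming the governing analysis would close the gap. This is fair, but that sentence still has to be written, together with a cut-off that fits the denominator chosen.

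**Conclusion.** The point holds in limited form. The rule is sized on patients with a month-6 IgG, a disease-related dropout reason is named, and failure coding is attached to neither boundary. Any bias runs in one direction, towards declaring an effect.

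With a true 20% rate among all enrolled, 10% dropout and both boundaries applied to completers, the inflation is ×1.0 to ×1.8 at the written cut-off and ×1.0 to ×2.0 at 11 of 31, depending on a share that the documents do not give. It is smaller if stage 1 already counts every enrolled patient. The 11-of-31 boundary has almost no slack (0.02498 against 0.025), so practically any share above zero takes it past the nominal level. The plan should settle this before the first decision, but the documents do not show that the false-positive rate will double.

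**What to change.** **Preferred.** In Section 9.0 of both protocol and SAP, base both stage decisions on all patients who start lenalidomide and count a missing month-6 IgG as non-response, whatever the reason. Continue with at least 4 of the first 12 and declare success with at least 12 of 35. State whether the 50% target refers to all treated patients (power 0.917) or only to those who stay (0.830 at 10% dropout). Keep the completer analysis and the analysis of patients treated for 3 months or more as sensitivity analyses.

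**Minimum.** Keep 31 patients, count those who leave before month 6 for change in CLL status or toxicity as failures at both stages, and replace only administrative losses. The final cut-off must still be reconciled with the stated 0.025.

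**Cost.** Enrolment stays at 35. The success boundary in the protocol changes, so this is an amendment needing the company and IRB review that the protocol prescribes, not an edit to the SAP alone. Under the less favourable assumption power falls below the planned 90%, and the plan should say so.
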